Study Purpose	The purpose of the study is to collect safety and efficacy data on the performance of the study stoma site accessory when used to prevent abdominal wall leakage for patients with a long term feeding tube. This accessory has been developed by the Cleveland Clinic and will be used for the first time in human subjects according to the labeled indication for clinical use in accordance with the Manufacturer's Instructions for Use based on other similar, FDA approved gastrostomy and jejunostomy enteral feeding tube accessory components. After providing informed consent, eligible patients will receive a study stoma site accessory during a feeding tube replacement procedure the patient is scheduled to have as a standard of care procedure.
Study Design	Single site, prospective, phase I, non-randomized safety and efficacy of feeding tube stoma site accessory for patients with enteral feeding tubes.
Primary Endpoints	Safety and efficacy of the study stoma site accessory as evidenced by successful study accessory placement at time of initial replacement procedure, post procedure adverse events including recurrence of any documented preprocedure [abdominal surface] condition and repeat intervention up to 6 months after the initial replacement procedure.
Secondary Endpoints	Patient Quality of Life is hypothesized to improve significantly with leak reduction, therefore various Quality of Life questionnaires will be collected at baseline, 2 weeks and 6 months or early termination.
Patient Population	 Inclusion Criteria: Male or female, aged ≥22 and ≤85. Note: Because the study accessory is designed for adult use, participants <22 years of age are excluded but will be eligible for future trials, if applicable. Ability to understand and the willingness to sign a written informed consent document.

	-

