	 Patients with existing gastrostomy and jejunostomy enteral feeding tubes, placed ≥ 3 months, undergoing replacement of feeding tube inpatient or outpatient. Willing to adhere to placement of study stoma site accessory and ability to take oral temperature at specified times. Stated willingness to comply with all study procedures and availability for the duration of the study. Willing to adhere to removal of study stoma site accessory at mo. 6 Exclusion Criteria Patient requires general anesthesia in an OR for tube changes Current use of steroids (any dose) daily ≥ 3 months including, but not limited to: prednisone, prednisolone, methylprednisolone, cyclosporine Current use of Immunosuppressants including, but not limited to: azathioprine, mycophenolate. BMI ≥ 40 Non-English speaking patients. Pregnant Women. Known allergic reactions to components of the study stoma site accessory: Medical Grade Silicone as described in Technical Data Prospectus from Dow Corning Corporation. Treatment with another investigational drug or device within 6 months of screening/baseline. Uncontrolled illness, recent open abdominal surgery or social situations that in the opinion of the investigative team would limit compliance with study requirements, including, but not limited to: Ongoing or active infection Psychiatric illness Unable to self-report Not ambulatory and incapable of carrying out all self-care Unsuccessful study accessory placement at initial replacement procedure
Number of	The study will enroll until 10 patients have had successful study stoma
	site accessory placement and reached the 2 week research follow-up
Subjects	visit.
Number of Sites	1
Sample Size	The sample size is 10 subjects. No formal sample size calculations were
Justification	performed for pre-market safety and efficacy data.
Study Hypothesis	The study is a pilot trial to access feasibility and safety with the aim to improve patient quality of life using pre and post measures. Patient quality of life assessment will be collected at baseline and 6 months for comparison.

Duration of Study	Expected enrollment period is 12 months. Follow-up duration is 6 months from initial replacement procedure with follow-up research visit at week 2 and phone calls at weeks 4 and 6 and month 6 and research visits at months 3, 4 and 6. The study will conclude 6 months from the enrollment of the last subject.

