Study Accessory and Technique Description

OVERALL DESIGN

[figure not shown]

Fig 1. From Left; ribbed accessory plug, retention bumper side view and view from top

This is a single site, prospective, phase 1 pilot study designed to evaluate the safety and efficacy of the study stoma site accessory when used to prevent abdominal wall leakage for patients with a long term, ≥ 3 months, enteral feeding tube, including gastrostomy or jejunostomy tubes. Outcomes of these patients will be evaluated based on collected measures of successful study accessory placement, incidence of reported adverse events and quality of life measures. Patients enrolled in the study will participate for a period of 6 months with outcomes assessed using our protocol patient questionnaires. The length of the study will be approximately 12-18 months to allow for recruitment, and 6 months of ongoing follow-up after the last patient is enrolled.

Proof of concept testing on the study stoma site accessory showed the accessory is effective at preventing leakage. Prototypes for the test were constructed by Cleveland Clinic Medical Device Solutions. A bench model of an artificial bladder with a balloon inside was used to simulate a stomach (Fig 2).

[figure not shown]

[figure not shown]

Fig 2. Control test without study accessory

For the control, a low profile feeding tube was placed in the stoma site without the study accessory. The bladder was filled with yellow dyed water and the balloon was inflated to increase pressure to the point of leakage.

In the control test without the study accessory, there was no pressure change nor build up because leakage occurred immediately through the space between "stoma" and the tube (Fig 2). For the bench test, the low profile feeding tube end was inserted into the study stoma site accessory and the assembly was placed in the bench model. With the study stoma site accessory, the bench model was pressurized up to 100mmHg. No leakage formed at the "Stoma Site." Leakage was seen from other parts of the model, such as the screws (Fig 3).

PRODUCT INFORMATION

- Custom components: Accessory retention bumper and plug with introducer
- Material: Dow Corning® QP1-250 Liquid Silicone Rubber
- Manufacturing: Injection molded in soft, medical-grade silicone. Two-part, platinum catalyzed.
- Quality: Raw materials are lot traced by ISO 9001-certified manufacturer, Proto Labs

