The patient may incur some expenses as a result of being in the study, such as hotel, food, bus/taxi fare and parking fees when attending scheduled or unscheduled visits. To assist with the cost of time and travel associated with study participation at CC, subjects will be paid \$50.00 for the completed week 2 interval assessment and again at early study termination and months 3, 4 for completed research visits and month 6 following removal of the study accessory and completion of patient questionnaires. Patients will be provided a parking voucher for the week 2 and months 3, 4 and 6 study visits attended in-person and compensated for their time and effort toward participation at the rate of \$50.[Table2] If, at any time prior to month 6, the patient experiences a repeat intervention scheduled at the Clinic with either a feeding tube change that requires removal of the study accessory and results in early termination the patient will be compensated at the rate of \$50 for their time and effort toward participation and provided a parking voucher. The Clinic is paying the study doctors and the study team for their work in this study. Subjects will be paid per the schedule below in the form of a check mailed to the patient's confirmed

Subjects will be paid per the schedule below in the form of a check mailed to the patient's confirmed residence.

Study Calendar Visits	Compensation Amount
Screening/Baseline visit with Consent	
Day 1 (Accessory Placement)	
Week 2 (Research Visit Assessment)	\$50.00
Week 4 (Phone Call)	
Week 6 (Phone Call)	
Month 3 (Research Visit Assessment)	\$50.00
Month 4 (Research Visit Assessment)	\$50.00
Unscheduled or Early Termination	\$50.00
Month 6 (Research Visit with Accessory	\$50.00
Removal and Completed Patient Questionnaires)	

Table 2 Overview of participant compensation

In the event of physical injury or illness resulting during participation in the study, medical care is available at the Cleveland Clinic, however, the Cleveland Clinic has no plans to provide free care or compensation for a patient's lost wages. The study participant and/or their insurance carrier will be responsible for all expenses related to the injury or illness.

Primary Outcome Measures

STUDY OBJECTIVES AND ENDPOINTS					
OBJECTIVES	ENDPOINTS	JUSTIFICATION FOR ENDPOINTS			
Primary					
Safety and efficacy of the study	Rate of procedural success will be	Demonstrate study			

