accessory as evidenced by rate of	defined as placement of the device at	accessory viability; its			
successful device placement and	the intended location, including securing	safety and efficacy for			
related post procedure adverse	of the device in place and its	use in a general			
events.	effectiveness at the week two [2] exam.	population of patients			

OBJECTIVES	ENDPOINTS	JUSTIFICATION FOR ENDPOINTS
The study will focus on the known minor risks of tube leakage associated with feeding tube components including recurrence of any documented pre-procedure [abdominal surface] condition, new condition or repeat intervention up to 6 months after the initial replacement procedure.	Patients will be followed up to 6 months after the index procedure. However, any patient who requires re-intervention that compromises the study stoma site accessory integrity (e.g., study accessory is removed and replaced with standard of care components or otherwise damaged) subsequent to the initial replacement procedure will no longer be followed but will be included in the analysis of the endpoints until the time of re-intervention. Rate of post-procedure adverse events to be collected from initial replacement procedure through month 6, including but not limited to: Dermatitis Cellulitis Accessory migration over 1 cm An adverse event determined as related or possibly related Allergic reaction to the accessory material	displaying a broad range of disease processes for which they will be receiving EN or HEN for ≥ 3 months.
Secondary		
Change in patient quality of life after intervention as self-reported by participants. Outcomes will be collected at various intervals.	Various participant reported outcomes will be collected at baseline, week 2 and month 6: PROMIS 10, nationally validated quality of life survey tool Alcohol/ tobacco use Study accessory management questions Characteristics of pain and leakage at site of study accessory placement	Demonstrated ability to predict clinical benefit to patients with enteral feeding tubes.

Table 3

Hypothesis Testing

This is not a hypothesis driven study. The study is a pilot trial to determine safety and efficacy of a feeding tube accessory and feasibility of determining improvement of patient quality of life using pre and post measures. Patient quality of life assessment will be collected at baseline and 6 months for comparison.

Data Collection and Analysis

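### The placement-success part of the primary endpoint is timed at the procedure in the synopsis but also needs undefined week-2 effectiveness in Table 3, and the synopsis rate is 100% by construction

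*Combined protocol and SAP*

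**What the plan says.** - **Protocol Synopsis, Primary Endpoints.** Safety and efficacy are to be shown by "successful study accessory placement at time of initial replacement procedure". The same sentence adds post-procedure adverse events, including return of an earlier abdominal-surface condition, and repeat intervention over 6 months.
- **Primary Outcome Measures, Table 3.** The endpoint column begins "Rate of procedural success will be" and continues "defined as placement of the device at" and "the intended location, including securing". It ends by requiring the device's "effectiveness at the week two [2] exam". The objective column of the same row mentions only the rate of successful placement.
- **Overall Design.** "Outcomes of these patients will be evaluated based on collected measures of successful study accessory placement", alongside adverse events and quality of life. Week 2 is not mentioned.
- **Synopsis, Number of Subjects and Sample Size Justification.** "The study will enroll until 10 patients have had successful study stoma" accessory placement and have reached the week-2 visit. "The sample size is 10 subjects. No formal sample size calculations were" performed.
- **Exclusion criteria (synopsis and main text).** Unsuccessful placement at the initial procedure is listed as an exclusion.
- **Number of patients; Early Patient Withdrawal.** Patients withdrawn before the week-2 visit are replaced until 10 have passed it.
- **Data Collection and Analysis.** Endpoints are summarised as counts and percentages with 95% confidence intervals. No interval method, denominator or success criterion is given.

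**The concern.** The two texts differ on the outcome that the accessory is meant to change. Its purpose is to prevent leakage, and leakage at week 2 is what separates them. The synopsis wording is more than a shortened form of Table 3, because it names its own time point, the procedure itself. With no order of precedence and no criterion for effectiveness, whoever reports the study can choose the numerator after seeing the data. In a study without a hypothesis test, the prespecified definition is the main protection against that choice.

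The enrolment rule makes this worse. If the 10 counted patients are defined by successful placement, the proportion of them successfully placed carries no information.

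**Working it through.** **What differs.** Table 3 appears to add two conditions to the synopsis, securing and week-2 effectiveness. Step 15 of the Instructions for use already makes secure seating of the bumper part of placement, so securing adds nothing new. The real difference is effectiveness at week 2.

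**Who can separate the two rates among the 10.** Under Adverse Events and Serious Adverse Events Reporting, a patient whose accessory is lost or compromised and is replaced by a commercial one leaves the study. If that happens before week 2, the patient is replaced and is not one of the 10. Only a patient who keeps the accessory and leaks at week 2 counts differently under the two texts.

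**Inputs.** n = 10 comes from the synopsis, without a calculation, so there is no planned figure to reproduce. The documents give no expected leakage rate, so the number of leakers k is assumed. No interval method is named, so exact (Clopper-Pearson) intervals are used.

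**Synopsis rate.** All 10 counted patients were placed successfully by definition, so the rate is 10/10 = 100%. The exact lower limit is 0.025^(1/10) = 0.692, which gives 69.2-100%.

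**Table 3 rate.** This is (10 − k)/10, with limits from the beta quantiles B(0.025; x, n − x + 1) and B(0.975; x + 1, n − x), where x = 10 − k:

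| Assumed leakers k | Synopsis rate | Table 3 rate | Exact 95% CI, Table 3 |
|---|---|---|---|
| 0 | 100% | 100% | 69.2-100% |
| 1 | 100% | 90% | 55.5-99.7% |
| 2 | 100% | 80% | 44.4-97.5% |
| 3 | 100% | 70% | 34.8-93.3% |

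**How likely the rates are to differ.** Suppose each placed patient is effective at week 2 independently with probability q. The chance of at least one discordant patient is 1 − q^10:

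- q = 0.95: 1 − 0.599 = 40%
- q = 0.90: 1 − 0.349 = 65%
- q = 0.80: 1 − 0.107 = 89%
- q = 0.70: 1 − 0.028 = 97%

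**Effect of counting every attempt.** With 1 or 2 assumed placement failures before 10 successes, the placement rate is 10/11 = 90.9% (58.7-99.8%) or 10/12 = 83.3% (51.6-97.9%). It can then take values other than 100%. With 12 attempts and 2 of the 10 placed patients leaking, the week-2 rate is 8/12 = 66.7% (34.9-90.1%).

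**The case against.** The strongest reply is that only Table 3 claims to define the rate. The synopsis lists kinds of evidence, and Table 3's own objective column sets the short phrase beside the full definition, so Table 3 can naturally be read as governing. That lessens the conflict but does not remove it: the synopsis fixes a different time point, no section gives precedence, and effectiveness has no criterion even if Table 3 governs.

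A second reply is that the study is a descriptive pilot with no threshold tied to this rate. That is correct and limits the severity.

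A reader might also infer more than the documents support:

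- **That the synopsis endpoint ignores efficacy.** It does not. The same sentence covers recurrence of abdominal-surface conditions and repeat intervention, and leakage is asked about at week 2 and at later contacts. What is missing is a clear place in the synopsis endpoint for leakage that causes neither a skin condition nor a re-intervention.
- **That early device loss separates the two rates in the same 10 patients.** The exit and replacement rules normally take such patients out of the 10.
- **That securing is a further discrepancy.** The placement instructions already include it.

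**Conclusion.** The inconsistency is real, and it comes down to week-2 effectiveness, which is required in Table 3, absent from the synopsis and defined nowhere. Among the 10 counted patients the synopsis rate is fixed at 100% (exact 95% CI 69.2-100%), while the Table 3 rate loses 10 points for each patient who keeps the accessory but leaks. The two agree only if nobody does.

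The 100% figure follows from the enrolment and exclusion rules if the 10 counted patients are the denominator. Adding patients who were placed but withdrew before week 2 would leave it at 100%; only counting failed placements can lower it. The leaker counts and the values of q are assumptions.

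This should be fixed before analysis. It would be too strong to say that it invalidates the study or a decision, because the plan states no test, alpha, power or go/no-go rule that depends on this rate.

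**What to change.** Replace the single item by two named rates, worded identically in the synopsis and Table 3:

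1. **Technical success:** accessory placed and secured on Day 1, over all patients in whom placement was attempted.
2. **Week-2 success:** accessory in place and a prespecified leakage criterion met at week 2, over the same denominator. Patients who leave before week 2 count as not successful, with reasons listed. The investigators should set the criterion from the pain-and-leakage questionnaire and stoma inspection.

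Report both with exact 95% confidence intervals. For analysis purposes, take unsuccessful placement off the exclusion list, and state that replaced patients stay in the denominator. Patients ruled out before any attempt remain screen failures, as the protocol already provides.

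No new visit or measurement is needed, since the schedule of events already includes both week-2 assessments. The cost is wording in four places (synopsis, Table 3, exclusion text, replacement text), one extra row in the results table, and a headline rate that may be noticeably less favourable than 100%.
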